5.3.9 Missing Data and Outliers

5.3.9.1 Missing data

A missing data point for a given study visit may be due to any one of the following reasons:

- The visit did not occur
- The visit occurred but data were not collected or were unusable
- The patient permanently discontinued from the study before reaching the window for the study visit

In general, missing baseline data will not be imputed. The following approaches are default methods for missing data handling in summary tables:

- Categorical data at baseline will be summarized for each treatment arm using counts (n) and percentages (%). Unless otherwise specified, denominators for all percentages will be the total number of patients in the corresponding treatment arm and dose number (if applicable) within the population of interest.
- Continuous data: The analyses and summaries for variables with continuous scales will be based on observed data only. Only available data will be used.
- In general, change from baseline is calculated only for patients with non-missing values for both the baseline and the time-point of interest and will be missing otherwise.

Missing data commonly encountered during the study may comprise:

- Missing/Partial Dates: For incomplete days or months, an imputation will be done by assigning the first day of month or the first month of year, respectively. For incomplete years in dates for measurements after randomization, the year of first dose date will be assigned.
- Continuous variables: mixed models are robust to the presence of missing at random and conducts the analysis with all participants despite the presence of missingness. Of note, this method calculates the estimations based on the variance-covariance structure but without any formal imputations.

Missing data commonly encountered for safety and background variables may comprise:

- Missing/Partial Dates for AEs:

Missing or partial AE onset dates and times will be imputed so that if the partial AE onset date/time information does not indicate that the AE started prior to treatment or after the TEAE

period, the AE will be classified as treatment-emergent. These data imputations are for categorization purpose only and will not be used in listings. No imputation is planned for date/time of AE resolution.

Missing/Partial Dates for Concomitant Medications:

No imputation for medication start/end dates or times will be performed. If a medication date or time is missing or partially missing and it cannot be determined whether it was taken prior or concomitantly, it will be considered a both prior and concomitant.

Only for immunosuppressive medications, vaccines, and new HBV treatments or medications associated with MAEs, NCIs, SAEs, hepatitis flares, or hepatic injury that can be recorded beyond Day 169, it will also be considered as post-treatment.

Handling of Missing Assessment of Relationship of AEs to IP

If the assessment of the relationship to IP is missing, then the relationship to IP in the frequency tables is considered as "possibly related", but no imputation should be done at the data level.

Handling of Missing Severity of AEs

If the severity is missing for some of the treatment-emergent occurrences of an AE, the maximum severity on the registered occurrences will be considered. If the severity is missing for all the occurrences, a "missing" category will be added in the summary table.

Handling of Missing values in WBC differentials

For abnormalities reported only for one in the pair "absolute counts or percentages" in any of the WBC differentials (Basophils, Eosinophils, Lymphocytes, Monocytes, Neutrophils), the same level of abnormalities will be imputed for the other in the pair.

If any of the WBC differentials in absolute count or percentage is missing, it will be imputed from the total WBC value following the rule "Absolute values are calculated by multiplying the total number of WBCs by the percentage of each type of while cell".

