5. POPULATION

5.1. Number of Patients

Approximately 80 patients are planned for enrollment over approximately 24 months at approximately 35 study centers in North America, Europe, UK and Asia-Pacific.

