6.3. Dose and Administration

HepTcell or normal saline placebo will be administered by IM injection at intervals of 4 weeks for 6 doses. Doses will be administered on Days 1, 29, 57, 85, 113, and 141 (±2 days for each dose). The 1.0 mL HepTcell injection contains 0.150 mg of each FP-02.2 peptide and IC31 at 500 nmol KLK and 20 nmol ODN1a.

Each dose of HepTcell or placebo will be administered as an IM injection (1.0 mL) in the deltoid muscle, where possible, of the non-dominant arm by appropriately trained clinical staff members. Patients will stay in the unit for at least 2 hours following administration of the first and second doses. Vital signs will be assessed before dosing and every 15 minutes post dosing over 2 hours at these two visits, and medications and qualified medical personnel will be available in case a patient experiences a severe acute allergic reaction during the immediate post-vaccination period.

Refer to ALT-301-202 Pharmacy Manual for specific preparation information and country specific procedures (if applicable).

If an authorized COVID-19 vaccine has been administered in proximity to a scheduled IP administration, a ± 3 day window is allowed for IP dosing.

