7. PREMATURE DISCONTINUATION

7.1. Individual Patients

Patients can choose to discontinue study medication or participation in the study at any time, for any reason, without prejudice to their future medical care. Patients could be discontinued for any of the following reasons:

- Patient request/withdrawal of consent
- Noncompliance with study requirements
- Loss to follow-up
- Investigator discretion
- Sponsor request, including termination of the study by the Sponsor

In case of worsening or disease progression, study medication will be discontinued, and the medications prohibited in Section 6.7.1 will be allowed, at the discretion of the investigator and Sponsor, if it is in the patient's best interest to initiate any treatment prohibited in the study.

If a patient prematurely discontinues study medication before Day 169, Day 169/ET procedures will be performed. Patients who prematurely discontinue study medication will remain in the study for Follow-up Period study assessments, with the dates of visits adjusted to correspond to 13, 26, 39 and 52 weeks after the last dose of study medication.

Eligible patients who are randomized and withdrawn before their second dose of study medication will be replaced. Patients who have received two doses of study medication who are subsequently withdrawn from the study will not be replaced.

In consultation with the DMC, patients in the Sentinel Cohort may be replaced at any time to assure that the reliability and integrity of the data from this cohort remains intact.

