If a patient prematurely discontinues study medication on or before Day 169, the Day 169/Early termination procedures will be performed. Patients who prematurely discontinue study medication will remain in the study for follow-on study assessments.

Patients will be followed for 52 weeks after the last dose of study medication (504 days beyond Day 1 for patients who complete the 24-week Treatment Period). AEs and concomitant medications will be recorded from the signing of informed consent to Day 169, but only MAEs, NCIs, and IMCs, which will be categorized as AEs, will be followed subsequently. Likewise, concomitant medications will be recorded through Day 169, but only immunosuppressive medications, vaccines, and new HBV treatments or medications associated with MAEs, NCIs, SAEs, hepatitis flares, or hepatic injury will be recorded beyond this point. At the end of the clinical trial, the decision about follow-on treatments and medical care will be made by the patient's medical physician or medical team in accordance with the usual standard of care.

Risk-factor analysis and appropriate surveillance for hepatocellular carcinoma (HCC) may be performed at the discretion of the investigator.

Study Schematic

Each patient will participate in the study up to approximately 77 weeks (a 5-week Screening Period, a 24-week Treatment Period, and a 52-week Follow-up Period commencing after the last dose of study medication at Week 20).

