5.3.3.12 Laboratory Evaluation

Hematology (including white blood cells (WBC), red blood cells, hemoglobin, hematocrit, mean corpuscular volume, mean corpuscular hemoglobin, mean corpuscular hemoglobin concentration, platelets, WBC differential (absolute and %), neutrophils, lymphocytes, monocytes, eosinophils, basophils); Liver Panel (including total and direct bilirubin, AST, ALT, total protein, albumin, GGT, lactate dehydrogenase, AP, INR); Serum Chemistry (including sodium, potassium, urea, creatinine, calcium, phosphate, glucose, creatine kinase) will be evaluated at each scheduled visit day during treatment period, as well as the scheduled days during Treatment follow-up period.

Urinalysis (including protein, bilirubin, urobilinogen, ketones, glucose, leukocyte esterase, red blood cells, pH, nitrites, specific gravity, microscopy) will only be evaluated in the same days during treatment period but not during the Treatment follow-up period.

The summary statistics (including number, mean, SD, median, Q1, Q3, minimum, and maximum) of all quantitative laboratory variables (laboratory values and changes from baseline) will be calculated for each dose during the treatment period and for each visit during the follow-up period, by treatment arm.

Laboratory data will be analyzed at pre-doses of Dose 1 to 6. For all parameters, the last available measurement after last dose and before the current dose will be the representative value to be summarized for each dose (ie: for dose 2, last value taken from "Date of dose 1 + 1 day until Date of dose 2").

For each visit during the follow-up period, the last of all measurements for the corresponding visit will be the representative value to be summarized.

The number (%) of patients with abnormal results (out of normal range) for each of the laboratory variables will be summarized at pre-dose of Doses 1 to 6 and in each visit during the follow-up period and treatment arm

22-Apr-2024

Shift tables for baseline versus each pre-dose for Doses 1 to 6 and follow-up visits will be presented for the hematology, urinallysis and chemistry laboratory parameters.

Data collected for Microscopy in Urinalysis (if clinically indicated or hemoglobin is detected on dipstick) will only be listed.

Data will be listed by patient.

Only available data will be used, and missing data will not be imputed.

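### A measurement date with a missing year is given the year of first dose, so some treatment-period samples would be dated before dosing began

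*SAP*

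**What the plan says.** SAP 5.3.9.1 has two rules for partial dates in general. For a missing day or month: "For incomplete days or months, an imputation will be done by assigning the first day of month or the first month of year, respectively". For a missing year: "For incomplete years in dates for measurements after randomization, the year of first dose date will be assigned". Neither refers to the visit, and neither stops the result from falling before the first dose.

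Two kinds of date are handled separately in the same section. Partial adverse event onset dates are imputed only to classify the event and are kept out of listings. For medications, "No imputation for medication start/end dates or times will be performed". The general rules therefore cover the remaining dated measurements, such as laboratory, virology and vital-sign dates.

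Two derivations depend on these dates. For laboratory parameters in SAP 5.3.3.12, "the last available measurement after last dose and before the current dose will be the representative value to be summarized for each dose", with the window set by dose dates. In SAP 4.3, flare duration is the stop sample date minus the start sample date, plus one.

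**The concern.** Dosing and follow-up run well past a calendar year-end for many patients: SAP 2.3 puts the end of follow-up at "504 days beyond Day 1 for patients who complete the 24-week Treatment Period". A fixed assignment to the first-dose year moves every measurement from a later year back by at least one year. A post-dose sample can then carry a date before the patient was treated, and any derivation that selects or subtracts by date will mishandle it. The stated rule creates this contradiction, because the visit at which the sample was taken already shows that the date is impossible.

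**Working it through.** **Timing.** The last dose is at Week 20, which is 20 × 7 = 140 days after Day 1. Adding 52 weeks gives 140 + 364 = 504 days, which reproduces the plan's figure (Day 505). The 39-week follow-up visit is at 140 + 273 = 413 days (Day 414).

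**How often the assigned year is wrong.** The year is wrong when the visit falls in a later calendar year than the first dose. This needs no assumption for a single patient: Day 85 (84 days later) is affected when the first dose is on or after 9 October, and Day 169 (168 days later) when it is on or after 17 July. To turn this into a share, I assume that first doses are spread evenly over the year. The Protocol (5.1) makes that reasonable but does not guarantee it: "Approximately 80 patients are planned for enrollment over approximately 24 months". With d days after first dose, the share is min(1, d/365.25). Enumerating all 1,461 first-dose dates in a four-year cycle gives the same values.

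| Visit | d | Year wrong | Imputed date before first dose |
|---|---|---|---|
| Day 29 | 28 | 7.7% | 7.7% |
| Day 57 | 56 | 15.3% | 15.3% |
| Day 85 | 84 | 23.0% | 23.0% |
| Day 113 | 112 | 30.7% | 30.7% |
| Day 141 | 140 | 38.3% | 38.3% |
| Day 169 | 168 | 46.0% | 46.0% |
| Day 232 | 231 | 63.2% | 63.2% |
| Day 323 | 322 | 88.2% | 88.2% |
| Day 414 | 413 | 100% | 13.1% |
| Day 505 | 504 | 100% | 38.0% |

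Up to Day 323 the gap is under a year, so a wrong year always puts the date before dosing. At Days 414 and 505 the gap exceeds 366 days even at the early edge of the ±10-day window (403 and 494 days), so the first-dose year is never possible. All percentages are conditional on the year being missing.

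**Laboratory window (constructed example).** First dose 15 October 2022; dose 3 (Day 57) is 10 December 2022 and dose 4 (Day 85) is 7 January 2023. The window for dose 4 runs from 11 December 2022 to 7 January 2023. A sample dated 7 January with no year becomes 7 January 2022, which is 281 days before first dose and outside the window. Table 1 of the Protocol schedules one safety sample in each of the windows for doses 4, 5 and 6, so the pre-dose value is lost unless an extra sample was drawn. For doses 2 and 3 the Day 8 or Day 36 value would replace it. Day 169 follows the last dose and feeds no between-dose window; its 46% matters for flare dates.

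**Flare duration (constructed example).** First dose 1 September 2022. A flare starts on Day 113 (22 December 2022) and stops on Day 141 (19 January 2023, year missing).
- True duration: 28 + 1 = 29 days.
- Under the rule the stop date is 19 January 2022, which is 337 days before the start: −337 + 1 = −336 days.

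**Day and month rule.** It also lacks a floor. If only the year is known, 1 January of the true year precedes first dose for 76.7% of first-dose dates at Day 85 and 53.7% at Day 169. If the whole date is missing, the two rules give 1 January of the first-dose year, before dosing for 99.7%.

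**The case against.** The strongest reply is that almost nothing reported depends on this rule.

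- **Frequency.** Protocol 11.1, 11.5 and 11.7 require missing data to be queried and explained, so yearless measurement dates should be rare. This stands; the documents give no rate.
- **Follow-up.** A reader might infer from the 100% figures that follow-up results are corrupted. They are not. The SAP index stops the haematology, biochemistry, vital-sign, ECG, weight and targeted-examination tables at Day 169. Its follow-up tables cover medically attended events, new-onset chronic illnesses and immune-mediated conditions, whose onset dates have their own rule. Only listings remain. Nor is the year wrong for every visit in those slots: after early discontinuation, visits are "adjusted to correspond to 13, 26, 39 and 52 weeks after the last dose of study medication". A 39-week visit after one to four doses (Days 274 to 358), or a 52-week visit after one dose (Day 365), can fall in the first-dose year.
- **Baseline.** A reader might infer that misdated values become baseline. SAP 4.1 takes the most recent value up to first dose, and a Day 1 or screening value would normally be more recent than a date moved back by a year.
- **Day 8 samples.** With the day missing, such a sample is often moved to or before first dose, but it is not the value selected for dose 2 when the Day 29 sample exists.
- **Visit-keyed analyses.** The primary and secondary endpoints are defined at Days 85 and 169, and vital signs are summarized by visit. Neither is exposed.
- **Flare safeguard.** SAP 4.3 uses the visit date when there is no sample date. That helps when the date is absent, but it does not clearly cover a partial one.

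These points narrow the scope. They do not make the rule correct, and I found no other section that overrides it.

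**Conclusion.** The rule is wrong as written, with small practical effect. When it is triggered for a treatment-period visit that crosses a year-end, the imputed date precedes dosing: about 23% of Day 85 dates and 46% of Day 169 dates, assuming evenly spread first doses and given that the year is missing. The consequences are a lost or substituted between-dose laboratory value and a possible negative flare duration. The latter needs a qualifying flare, a yearless stop date and a year-end between start and stop. Any measurement on true study Day 414 or 505 would get an impossible year, which reaches listings at most. The documents do not support extending the point to efficacy results, follow-up tables or, in normal circumstances, baseline.

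**What to change.** Replace the general partial-date rules for post-randomization measurements in SAP 5.3.9.1 with one sentence: keep the known date parts, impute the missing parts from the first dose date plus the nominal visit day, bounded by the adjacent visit dates and never earlier than first dose for a post-dose visit. An equally acceptable alternative is to leave the date missing and assign the record by its visit label; a flare duration that needs that date would then be reported as missing.

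The cost is one sentence and a small programming change. SAP version 2.0 states that the Week 24 analysis has been done, so also check whether any laboratory date in it had a missing year. If none did, no output changes.

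### The SAP copies an abnormality flag between the absolute and percentage white-cell differentials, so an in-range value can be tabulated as abnormal

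*SAP*

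**What the plan says.** SAP 5.3.9.1, under the sub-heading "Handling of Missing values in WBC differentials", gives two rules for basophils, eosinophils, lymphocytes, monocytes and neutrophils.

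- **Flag rule.** "For abnormalities reported only for one in the pair" (absolute count or percentage), "the same level of abnormalities will be imputed for the other in the pair".
- **Value rule.** "If any of the WBC differentials in absolute count or percentage is missing, it will be imputed from the total WBC value", using this relation: "Absolute values are calculated by multiplying the total number of WBCs by the percentage of each type of while cell" (the last phrase is a typing slip for white cell).

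SAP 5.3.3.12 lists the differential on both scales in the haematology panel and defines what is tabulated: "The number (%) of patients with abnormal results (out of normal range) for each of the laboratory variables will be summarized". It also plans shift tables from baseline. It ends by saying that only available data are used and that missing laboratory data are not imputed.

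SAP Appendix 1 includes the haematology abnormality table (14.3.4.1.2) and shift table (14.3.4.1.3) in the final report, through Day 169, on the safety population.

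**The concern.** The flag rule treats the two scales as if they shared one normal or abnormal status. They do not: the absolute count is the percentage multiplied by total WBC, and each scale has its own reference range. A raised lymphocyte percentage with an ordinary lymphocyte count is a normal arithmetical outcome when WBC is modest. Copying the flag would record that ordinary count as high.

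The copy is also unnecessary. Where one member is absent, the value rule supplies it, and the supplied value can be judged against its own range. The flag rule can therefore contradict the value that the SAP has just derived.

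At stake is the accuracy of the abnormality counts and shift tables for five cell types on two scales. The product is an immunostimulatory vaccine, so these tables are a relevant safety output, though not a central one.

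**Working it through.** The plan states no figure on this point, so there is nothing to reproduce. The check uses the SAP's own relation and asks whether the two scales can disagree.

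**Inputs.** From SAP 5.3.9.1: absolute count = total WBC × percentage / 100. From SAP 5.3.3.12: abnormal means outside the normal range for that variable. The documents give no reference ranges for differentials, so two sets are assumed (counts in ×10⁹/L).

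- Set A: lymphocytes 20–40% and 1.0–4.0; neutrophils 40–70% and 2.0–7.0.
- Set B: lymphocytes 20–45% and 1.0–4.8; neutrophils 45–75% and 1.5–8.0.

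**Step 1: single cases (set A, lymphocytes).**

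| WBC | % | Count | True flag, % | True flag, count | Flag rule gives |
|---|---|---|---|---|---|
| 5.0 | 45 | 5.0 × 0.45 = 2.25 | High | Normal | count High |
| 3.5 | 25 | 3.5 × 0.25 = 0.875 | Normal | Low | % Low |
| 11.0 | 38 | 11.0 × 0.38 = 4.18 | Normal | High | % High |

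**Step 2: how wide the discordant bands are.** Whole percentages from 1 to 99 were classified at WBC 3.5, 4, 5, 6, 8, 10 and 11.

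- Percentage abnormal, count normal: this occurs at every WBC tested, for both cell types and both sets. At WBC 5.0 under set A, the bands are lymphocytes 41–80% and neutrophils 71–99%.
- Percentage normal, count abnormal: this is less frequent and lies at low or high WBC. Under set A, lymphocytes of 20–28% at WBC 3.5 fall below 1.0, and lymphocytes of 37–40% at WBC 11 exceed 4.0. For neutrophils under set B it occurs only at WBC 11 (73–75%).

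**Step 3: apply the flag rule.** In each of these pairs exactly one scale is abnormal, so the rule is triggered and the in-range member becomes abnormal. The rule transfers only abnormalities, so no abnormal value becomes normal. The number of abnormal flags can only rise. In a shift table, an added flag at baseline can also hide a true shift on that scale.

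**Step 4: the two readings.**

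- Literal: the trigger is an abnormality on one scale only. It does not require the other value to be absent, and absent values have their own sentence. Every discordant pair is affected.
- Under the heading: only pairs with one member unreported are affected. Take the first row of the table with the count missing. The value rule derives 2.25, which is in range, while the flag rule attaches High to it.

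**Step 5: compare with 5.3.3.12.** A copied flag is not a result outside that variable's range, so it does not meet the tabulated definition. Both rules in 5.3.9.1 also impute, which 5.3.3.12 rules out for laboratory data.

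**The case against.** The strongest reply is that the sentence must be read in place. It stands in a missing-data section, under a heading about missing values, and its verb is impute. On that reading it fills an absent classification and does not overwrite a measured, in-range value that has its own flag. This is plausible, and it makes the effect much smaller, because it then scales with the fraction of one-sided reports, which the documents do not give. It does not remove the fault, since the derived value can still be in range under a copied flag.

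The practical stakes are also low, and that stands. Individual results are listed by patient. Protocol 9.4 makes a laboratory finding an adverse event on the investigator's judgement of a confirmed abnormality, not on this flag. No white-cell measure is in the stopping rules (Protocol 7.1.1). The study has been terminated, and the SAP addendum's supplementary outputs contain no haematology abnormality or shift table.

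A reader might infer more than the documents support:

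- **That abnormal values are hidden.** The rule never turns an abnormal flag into a normal one.
- **That a percentage inflation can be stated.** Such a figure needs the literal reading plus assumed ranges and distributions. With neutrophil ranges of 40–75% and 1.8–7.5, a lognormal WBC with CV 25%, and copying in every discordant pair, abnormal absolute-neutrophil results go from 8.4% to 9.4% (mean WBC 5.0, neutrophils 55 ± 7%) or from 4.2% to 11.1% (mean WBC 6.0, 55 ± 10%). The rise is 1.0 or 6.9 points depending on inputs that the documents do not contain.
- **That the entry criteria make discordance common.** Exclusion 10 sets a WBC floor of 3,500/µL. The 2,500/µL allowance applies only to individuals of African descent with neutrophils of at least 1,000/µL and no other identified cause of leukopenia. Nothing in the documents says how many such patients enrol.

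**Conclusion.** The point holds as a minor fault in a safety-table rule. SAP 5.3.9.1 allows an in-range absolute count or percentage to be tabulated as abnormal, and it conflicts with SAP 5.3.3.12 both on what counts as abnormal and on whether laboratory data are imputed. This follows from the SAP's own relation between the scales and needs only that each scale has its own reference range; the numerical bands above are illustrations under assumed ranges.

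The flags can err only towards over-reporting. The effect is confined to the haematology abnormality and shift tables for five cell types, applies to both arms, and does not reach any efficacy endpoint. Its size cannot be computed from the documents. It is larger if the sentence is applied to all discordant pairs and probably small if it is applied only to unreported members.

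**What to change.** In SAP 5.3.9.1, delete the flag-copying sentence and state the following:

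1. Where one member of the pair is missing, derive it from total WBC: count = WBC × percentage / 100, or percentage = 100 × count / WBC.
2. Flag each scale only against its own laboratory reference range, whether the value is measured or derived.
3. Where the missing member cannot be derived because WBC is also missing, leave its flag missing.

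In SAP 5.3.3.12, amend the sentence that rules out imputation so that it allows this one derivation.

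The cost is one deleted sentence, one amended sentence and a simpler derivation. The drawback is that haematology abnormality and shift tables already produced for the Week 24 analysis may need a rerun, or a footnote stating how the flags were assigned.
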